10.4.3 ANALYSIS OF THE SECONDARY ENDPOINT(S)

Clinical Decision Support System (CDSS)

Optimal programming of the spinal cord stimulator system is seen as a major future barrier to future widespread use, and, as a result, a major goal and specific secondary outcome of the study is exploration of the parameter space of epidural spinal cord stimulation. Current implantable pulse generators offer frequency, pulse width, amplitude, and electrode configuration as programmable parameters of continuous stimulation. While our expectation of future systems is increased freedom in the parameter space with more numerous parameters, more than 32 million settings can currently be programmed, far exceeding the number of parameters that could be evaluated in any clinical trial.

To overcome this daunting barrier to future clinical use, this study intends to populate a probabilistic model of the parameter space that is able to grow with the addition of each patient. Subthreshold testing of the stimulator system during clinical visits reduces the dimensionality of the parameter space by eliminating amplitude as significant, leaving frequency and pulse width.

At each visit, subjects will be assigned 8 randomly chosen clusters from the parameter space as a basis for response surface modeling. Subjects will be programmed 8 randomly sorted settings corresponding to one sample from each of the 8 clusters at each clinical appointment. During the month between clinical appointments, subjects will link their home volitional movement testing to the scheduled setting, which will assess velocity of their movements and fidelity of movement through randomized cuing. In turn, each setting will be assigned outcomes from their home testing. Each of the 8 settings will correspond to one of the 8 clusters being evaluated in the parameter space and each monthly visit will evaluate nearest neighbor settings until the response surface gradient can be calculated. Once the corresponding response surface gradient can be calculated, subjects will be programmed to descend the gradient until the end of the trial.

More specifically, the St. Jude Medical Proclaim Elite neurostimulators currently offer the following parameters:

Frequency: 2-100 Hz by 2s = 50 settings, 110 - 1200 by 10 = 110 settings

Pulse Width: 10-1000 us by 10: 100 settings

Amplitude: 0-25.5 by 0.1: 256 settings

These basic settings result in 4,096,000 possible settings. Up to 8 electrode groups can be given independent constant current settings out of the 16 electrodes implanted, resulting in 32,768,000 independent group electrode settings. Dimensionality reduction and global settings provide a space of 16,000 possibilities. The first generation of the clinical decision support system probabilistic model will evaluate this space.

Standing Training

Subjects will be assessed for ability to provide power during aided standing trials while wearing surface EMG electrodes. Average aggregate power generated will be calculated for the subject during the trial. Statistical testing will be by repeated measures ANOVA to examine for differences in mean.

The ANOVA residuals will be assessed for normality and the groups will be assessed for homoscedasticity. If there are significant violations of these assumptions then Friedman's test will be used instead. The data will be displayed with means and 95% confidence intervals between treatment and sham for each subject and as a group over time.

Missing data will be analyzed to examine for randomness of omission. If the missing data is determined to be reasonably random, then predictive mean matching will be used for imputation. The distribution of the complete data set will be examined with and without the imputed data.

Data from subjects with incomplete data from dropout will be included in the final analysis unless the subject requested removal of their data. Incomplete data will be pooled per session.

Autonomic Function

Multiple measures of autonomic function will be performed during autonomic appointments to characterize changes between stimulation and sham. Measurements made by ultrasound, continuous blood pressure measurement, or electrical response are all continuous measurements. Statistical testing will be by repeated measures ANOVA to examine for differences in mean:

- Sympathetic Skin Responses (SSR)
- Change in Cerebral blood flow (CBF) as measures by Transcranial Doppler during tilt testing
- Mean blood pressure during continuous noninvasive measurement
- Change in mean blood pressure during tilt testing
- Arterial stiffness
- Stroop test

The ANOVA residuals will be assessed for normality and the groups will be assessed for homoscedasticity. If there are significant violations of these assumptions then Friedman's test will be used instead. The data will be displayed with means and 95% confidence intervals between treatment and sham for each subject and as a group over time.

Missing data will be analyzed to examine for randomness of omission. If the missing data is determined to be reasonably random, then predictive mean matching will be used for imputation. The distribution of the complete data set will be examined with and without the imputed data.

Data from subjects with incomplete data from dropout will be included in the final analysis unless the subject requested removal of their data. Incomplete data will be pooled per session.

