4.2.2 SECONDARY ENDPOINTS

Secondary endpoints include:

1. sEMG power generated during standing
2. Classification of the parameter space
3. Cardiovascular system endpoints: blood pressure, cardiac function, arterial stiffness
4. Cerebral autoregulation and associated cognition

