For each participant, brachial BP will be measured (BpTRU-BPM-100, Coquitlam; VSM Medical, Vancouver, BC, Canada) on the right brachial artery. The following will be sampled at 1,000 Hz using an analog-to-digital converter (Powerlab/16SP ML 795; ADInstruments, CO Springs, CO, USA) interfaced with data acquisition software on a laptop computer (LabChart 7 ADInstruments): non-invasive beat-by-beat BP measurement via finger photoplethysmography (Finometer PRO, Finapres Medicine Systems, Amsterdam, The Netherlands), electrocardiogram (ML 132; ADInstruments), PETCO₂ (CO₂ Analyzer Gold Edition-17515, Ventura, CA, USA), velocity in the left middle cerebral artery (MCAv) or right posterior cerebral artery (PCAv; Doppler-Box, Compumedics DWL, Singen, Germany). These arteries will be insonated using a 2 MHz probe mounted on the temporal bone and a fitted head strap. As described in depth elsewhere, the P1 segment of the PCA will be insonated at depths between 60 to 70 mm, whereas the MCA was insonated from 45 to 55 mm. Arteries will be confirmed using ipsilateral common carotid artery compression, ensuring an increase in PCA velocity and decrease in MCA velocity. These metrics will be recorded throughout the aforementioned orthostatic sit-up test and following neurocognitive assessment.

Arterial Stiffness. 15 minutes.

aPWV (m/s) is calculated by dividing the distance between measurement sites, by the pulse transit time. Distance between the carotid and femoral arteries will be measured using measuring tape along the surface of the body, held parallel to the testing table. The pulse transit is determined from the arterial blood pressure waves, which are collected at each arterial site. A pen-like device (model SPT-301; Millar Instruments Inc., Houston, TX) will be applied to the carotid and femoral arterial sites using a light pressure to obtain arterial pressure waves. Heart rate will be recorded using a single-lead (lead I) electrocardiogram (ECG) (model ML 123, ADInstruments Inc., Colorado Springs, CO).

Arterial structure: Wall thickness and lumen diameter. 30 minutes.

Brachial and femoral arterial images will be collected using B-mode ultrasound (INFO) for 10 cardiac cycles. Images will be analyzed using internal ultrasound software to determine lumen diameter and intima-media thickness.

Test	Dependent variable	Evaluation of data	Comments

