10.2 STATISTICAL HYPOTHESES

Primary Endpoint

Volitional Response Index Magnitude

The hypothesis of the primary outcome VRI magnitude is that epidural spinal cord stimulation will provide a higher VRI magnitude than sham.

H0: mean treatment VRI magnitude = mean sham VRI magnitude

Ha: mean treatment VRI magnitude \neq mean sham VRI magnitude

Secondary Endpoints

Standing Training Assessment

Hypothesis: standing power will be improved with epidural stimulation

H0: mean treatment standing power = mean sham standing power

Ha: mean treatment standing power \neq mean sham standing power

Sympathetic Skin Responses (SSR)

Hypothesis: SSR will be unchanged by epidural stimulation

H0: mean treatment SSR = mean sham SSR

Ha: mean treatment SSR \neq mean sham SSR

Blood pressure

Hypothesis: blood pressure will be increased with epidural stimulation

H0: mean treatment BP = mean sham BP

Ha: mean treatment BP \neq mean sham BP

Cerebrovascular Assessment

Hypothesis: epidural stimulation will increased cerebral blood flow (CBF)

H0: mean treatment CBF = mean sham CBF

Ha: mean treatment CBF \neq mean sham CBF

Arterial Stiffness

Hypothesis: epidural stimulation will not change arterial stiffness (AS)

H0: mean treatment AS = mean sham AS

Ha: mean treatment AS \neq mean sham AS

Visual Neurocognitive Assessment

Hypothesis: epidural stimulation will improve Stroop score

H0: mean treatment score = mean sham score
Ha: mean treatment score != mean sham score

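### The planned tests of CBF change and arterial stiffness have no pressure term, so they leave the autoregulation endpoint unanswered and cannot separate a vessel change from a pressure change

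*Combined protocol and SAP*

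**What the plan says.** Section 4.2.2 lists "Cerebral autoregulation and associated cognition" among the secondary endpoints. Section 10.2 turns the cerebrovascular part into a hypothesis that stimulation increases CBF, tested as treatment mean against sham mean. The same section states "Hypothesis: blood pressure will be increased with epidural stimulation" and predicts that arterial stiffness will not change.

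For the autonomic endpoints, section 10.4.3 says "Statistical testing will be by repeated measures ANOVA to examine for differences in mean". The list that follows includes "Change in Cerebral blood flow (CBF) as measures by Transcranial Doppler during tilt testing", arterial stiffness, and two blood pressure variables (mean pressure during continuous measurement, and its change on tilt). Each is a separate outcome. No covariate, pressure-flow index or pressure-adjusted stiffness measure is named.

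The data collection goes further than the analysis. Under Cerebrovascular Assessment in section 7.1.1, the signals sampled with Doppler velocity include "non-invasive beat-by-beat BP measurement via finger photoplethysmography" and end-tidal CO2 (PETCO2). On timing it says "These metrics will be recorded throughout the aforementioned orthostatic sit-up test and following neurocognitive assessment". The test table in the same section describes autoregulation as Doppler flow in the middle and posterior cerebral arteries alongside beat-by-beat changes; the cell breaks off there. Velocity is taken from the left middle (MCA) or the right posterior (PCA) cerebral artery, and section 10.4.3 does not say which supplies the tilt contrast. aPWV is path length over transit time, and its procedure names only heart rate as a further recording.

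**The concern.** Autoregulation is a relation: how far flow changes when pressure changes. A variable that contains only flow cannot express it, particularly when stimulation is expected to alter pressure. Pressure swings are also likely in the subjects tested. Section 7.3.4 limits these visits to the autonomic dysfunction group, and the autonomic screening in section 7.1.1 uses systolic changes of 20 mmHg as its criterion.

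For aPWV, the plan predicts higher pressure and unchanged stiffness together. If aPWV depends on distending pressure, those two predictions can conflict in the raw measure even when the artery has not changed.

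At stake is interpretation. A CBF difference could be read as an autoregulatory effect, or an aPWV difference as a change in the artery, when either might only restate the blood pressure result. Timing matters too. Section 10.4.7.2 examines secondary outcomes after every six subjects and section 10.6.3 breaks the blind at interim analysis, so an index chosen later could be chosen with results in view.

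**Working it through.** The plan gives no effect size or sample size for these endpoints, so there is no figure of its own to reproduce. The 56 in section 10.5 is for the primary endpoint, and the size of the autonomic group is not stated. All inputs below are assumptions.

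**1. Can the planned CBF contrast identify autoregulation?** Let the index be k = (% change in velocity) / (% change in mean arterial pressure, MAP) from supine to upright. k = 0 means flow is fully held and k = 1 means it follows pressure. Use assumed falls of 20% and 10%.

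| Case | MAP fall, sham / stim | Velocity fall, sham / stim | CBF contrast | k, sham / stim |
|---|---|---|---|---|
| A: pressure effect only | 20 / 10 | 20 / 10 | 10 points | 1.0 / 1.0 |
| B: better autoregulation | 20 / 20 | 20 / 10 | 10 points | 1.0 / 0.5 |
| C: worse autoregulation | 20 / 10 | 10 / 10 | 0 | 0.5 / 1.0 |
| D: intact in both | 20 / 10 | 0 / 0 | 0 | 0 / 0 |

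A and B give the same planned contrast with different autoregulation. C and D both give no contrast, although autoregulation worsens in C. The pair (velocity change, MAP change) separates all four cases; velocity change alone does not.

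**2. How much could pressure alone move aPWV?** Assume wall modulus rises exponentially with pressure at rate z, so that aPWV is proportional to exp(zP/2), with z from 0.01 to 0.02 per mmHg and a starting value of 8 m/s.

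- Pressure rise at the reading of 0 mmHg: no change.
- 5 mmHg: exp(0.025) to exp(0.05), or +2.5% to +5.1% (0.20 to 0.41 m/s).
- 10 mmHg: exp(0.05) to exp(0.10), or +5.1% to +10.5% (0.41 to 0.84 m/s).

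The distance is measured parallel to the testing table, so the reading appears to be recumbent. The documents give no size for a recumbent pressure rise.

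**3. How often would a purely pressure-mediated difference be significant?** Simulate paired stimulation-minus-sham differences: d = b × (MAP difference) + error, error SD 1, MAP difference with SD 10 between subjects, no direct effect, two-sided 0.05, 2,000 trials per setting. The adjusted test is of the intercept when d is regressed on the MAP difference. Results for a mean rise of 10 mmHg:

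| n | b = 0.02 | b = 0.05 | b = 0.1 |
|---|---|---|---|
| 10 | 7% | 25% | 50% |
| 28 | 17% | 61% | 95% |
| 56 | 32% | 91% | 100% |

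Over mean rises of 5, 10 and 20 mmHg and the same slopes, the unadjusted rate runs from 5% to 98% (n = 10), 9% to 100% (n = 28) and 12% to 100% (n = 56). The adjusted test stays at about 4% to 6%. With b = 0 the unadjusted test also stays near 5%, so the problem exists only if the outcome depends on pressure.

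These rejections are not false positives for the total effect of stimulation. They become errors only if read as an autoregulatory or vessel effect.

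**4. What does adjustment cost?** In this model the adjusted standard error is about √(1 + D²/10²)/√n for a mean rise of D, and the unadjusted one is √(1 + 100b²)/√n. At b = 0.05 the unadjusted numerator is √1.25 = 1.12. For D = 5, 10 and 20 the adjusted numerators are 1.12, 1.41 and 2.24, so the adjusted interval is 1.00, 1.26 and 2.00 times as wide.

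**The case against.** The hypothesis in section 10.2 is that stimulation raises CBF. That is a total effect, and a sham-controlled comparison can test it without adjustment. Blood pressure is measured after stimulation starts, so conditioning on it asks a different question. This stands, and it is why the unadjusted CBF and aPWV contrasts should stay and neither adjusted result should replace them.

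Pressure is not ignored. Section 10.4.3 analyses its change on tilt in the same list, and the test table in section 7.1.1 connects autoregulation with beat-by-beat changes. The cut-off cell may have said more and cannot count against the plan. But the list in section 10.4.3 is intact, and two separate comparisons of means do not estimate a within-subject relation between pressure and flow.

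A reader might infer three stronger things that the documents do not support:

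- That these endpoints cannot be answered at all. Velocity, beat-by-beat pressure and PETCO2 are recorded together, so the autoregulation gap is in the specified analysis.
- That velocity simply follows pressure. That presupposes failed autoregulation, which the endpoint is meant to examine.
- That the planned variable runs opposite to the quality of autoregulation. It is a change on tilt, and for a given pressure fall better autoregulation gives a smaller velocity fall (case B). The variable is ambiguous, not reversed.

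Finally, section 10.4.9 calls secondary results preliminary. That limits the harm but does not supply the missing measure.

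**Conclusion.** The point holds as a gap between a named endpoint and its analysis. Followed as written, section 10.4.3 answers whether stimulation changes the CBF response in total and whether raw aPWV differs. It does not answer whether autoregulation differs, and it cannot say whether an aPWV difference lies in the artery or in the pressure.

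The CBF part rests on the definition of autoregulation and needs no assumed slope. The size of the aPWV part, and every rejection rate above, depends on slopes, pressure rises and group sizes that the documents do not give. At a slope of zero there is no distortion. This is a cheap improvement to secondary endpoints and does not affect the primary analysis.

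**What to change.** In section 10.4.3:

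1. Keep change in CBF as the test of the section 10.2 hypothesis. Add one pre-specified pressure-flow index as the autoregulation measure, for example % change in MCA velocity per % change in MAP from supine to upright, or transfer-function gain and phase from MAP to MCA velocity. Name the vessel and the postural manoeuvre, use the same ones under stimulation and sham, and include PETCO2 as a covariate. If the ratio is chosen, state how near-zero pressure changes are handled, because it becomes unstable there.
2. Report aPWV unadjusted (total effect) and adjusted for MAP taken at the reading, in the same posture and condition. Label the adjusted result a pressure-independent contrast that assumes a correct pressure slope and no shared causes of the pressure and aPWV changes. Do not interpret a raw aPWV difference as a change in the artery without it.

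Settle both before the first look at unblinded secondary data. The cost is SAP wording, some signal processing and analysis, and at most one cuff reading beside each aPWV recording; no new device or visit is needed. Adjusted intervals will be wider: little if the mean pressure rise is small against its between-subject spread, more if it is large.

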10.4.4 SAFETY ANALYSES

Safety Endpoints and a summary description are as follows:

- Physical Examination: signs of pressure ulcers, infections, or other relevant emergent findings
- Blood Pressure: change from baseline, before, and after stimulation sessions
- Adverse Event Incidence: as defined by 8.1 Specification of Safety Parameters
- Modified Ashworth Scale Score: changes from baseline, before, and after stimulation settings

Safety endpoints and adverse events will be presented via summary statistics after coding into System Organ Classes (SOCs). As applicable adverse events will only be coded once for each subject. Each adverse event will be described by start date, stop date, severity, relationship, outcome, and duration. AEs will be reported as outlined in 8 ASSESSMENT OF SAFETY.

10.4.5 ADHERENCE AND RETENTION ANALYSES

Most assessments are completed under direct guidance during clinical visits where results are immediately recorded. Compliance with the home rehabilitation program will be completed by measuring the percentage of completed assignments where assignments are at least 80% complete.

Subjects that do not meet this level of compliance will be detected during follow up visits, and they will be contacted upon missing any follow up visit. Subjects will continue to be followed regardless of compliance, which will be noted in data analysis. Subjects will be encouraged to improve compliance when necessary through help with scheduling and troubleshooting with training and rehabilitation.

10.4.6 BASELINE DESCRIPTIVE STATISTICS

Baseline characteristics will be described including demographics, medical history, and all baseline assessments of this single-arm study.

10.4.7 PLANNED INTERIM ANALYSES

10.4.7.1 SAFETY REVIEW

Safety review will be performed by the study monitor (Section 13.5) and analyzed by the Principal Investigator (Section 12.2). The procedure and scope of the safety monitoring parameters will be determined by the Principal Investigator.

10.4.7.2 EFFICACY REVIEW

In this open-label study, interim analysis will be completed after every cohort of six subjects to examine primary and secondary outcomes. These preliminary analyses will have no effect on subject enrollment or early termination of the study due to efficacy.

Formal interim analysis will occur after completion of final outcome of 30 and 60 subjects to assess for efficacy.

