5.5 PREMATURE TERMINATION OR SUSPENSION OF STUDY

This study may be temporarily suspended or prematurely terminated if there is sufficient reasonable cause. If the study is prematurely terminated or suspended, the PI will promptly inform the IRB and will provide the reason(s) for the termination or suspension. Circumstances that may warrant termination or suspension include, but are not limited to:

- Determination of unexpected, significant, or unacceptable risk to participants
- Demonstration of efficacy that would warrant stopping
- Insufficient compliance to protocol requirements
- Data that are not sufficiently complete and/or evaluable
- Determination of futility

Study may resume once concerns about safety, protocol compliance, data quality are addressed and satisfy the sponsor, IRB and/or FDA.

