The repeated measures ANOVA will be used to compare sham and treatment where alpha is assumed to be 0.025 (two tailed) and power 0.95. The correlation between repeated measures is assumed to be 0.5. The ANOVA residuals will be assessed for normality and the groups will be assessed for homoscedasticity. If there are significant violations of these assumptions then Friedman's test will be used instead. The data will be displayed with means and 95% confidence intervals between treatment and sham for each subject and as a group over time.

Missing data will be analyzed to examine for randomness of omission. If the missing data is determined to be reasonably random, then predictive mean matching will be used for imputation. The distribution of the complete data set will be examined with and without the imputed data.

Data from subjects with incomplete data from dropout will be included in the final analysis unless the subject requested removal of their data. Incomplete data will be pooled per session.

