10.4.9 MULTIPLE COMPARISON/MULTIPLICITY

There is only one primary endpoint for which this study is powered. Secondary and exploratory outcomes will provide preliminary information regarding these outcomes in subjects with chronic spinal cord injury undergoing epidural SCS.

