10.5 SAMPLE SIZE

Subjects will undergo blinded treatment and sham BMAC testing at each monthly appointment during the course of the trial. Assuming nonattendance to be approximately 25%, we expect subjects to complete at least 9 sessions. With a power of 0.95 and alpha of 0.025 for a two level ANOVA, we assume a correlation among repeat measure of 0.5. By assuming a baseline mean magnitude of 0.3 and a clinically significant change of 0.2 while assuming a within group standard deviation of 0.25 (resulting in an effect size of 0.4), we estimate that we will need at least 56 subjects to demonstrate significance for the primary outcome.

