10.6.3 BREAKING THE STUDY BLIND/PARTICIPANT CODE

Blinding will only be broken during interim and final data analysis.

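### The formal efficacy analyses at 30 and 60 completers have no boundary, per-look alpha or decision rule, so the type I error for the primary endpoint cannot be read from the plan

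*Combined protocol and SAP*

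**What the plan says.** Section 10.4.7.2 describes two kinds of interim analysis. The first is a review of outcomes after each cohort of six subjects, for which it says: "These preliminary analyses will have no effect on subject enrollment or early termination of the study due to efficacy". A separate paragraph then adds the formal analyses: "Formal interim analysis will occur after completion of final outcome of 30 and 60 subjects to assess for efficacy". Nothing more is said about them.

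Other sections that bear on the point:

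- Section 5.5, in a general list of circumstances that may lead to termination or suspension, includes "Demonstration of efficacy that would warrant stopping". It gives no criterion.
- Section 10.4.9, on multiplicity, says "There is only one primary endpoint for which this study is powered" and that secondary and exploratory outcomes are preliminary. It does not mention repeated analyses of the primary endpoint.
- Section 10.4.1 sets a general two-tailed level of 0.05. For the primary endpoint, Section 10.4.2 says "alpha is assumed to be 0.025 (two tailed) and power 0.95", and Section 10.5 repeats the figure: "With a power of 0.95 and alpha of 0.025 for a two level ANOVA".
- Section 10.5 concludes "we estimate that we will need at least 56 subjects to demonstrate significance for the primary outcome".
- Section 10.6.3 says "Blinding will only be broken during interim and final data analysis".

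**The concern.** Two formal tests of efficacy are planned on accumulating data, and the plan does not say what p-value counts as success at either, or what follows from it. The cohort-of-six disclaimer does not extend to the formal looks. With Section 5.5 open to stopping for efficacy, a success claim or a stop at 30 subjects is not excluded.

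The level of 0.025 is not labelled as the overall level or as the level for one look. These are different designs with different error rates. The blind is broken at interim analyses, so a rule written after the 30-subject look could depend on the results. A nominal p of 0.02 at 30 subjects could be declared a success or passed over, and either would comply with the plan as written. This affects the only endpoint for which the study is powered.

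**Working it through.** **Step 1. Does the sample size contain an allowance for interim looks?**

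Inputs from Section 10.5: change 0.2, SD 0.25, effect size f = 0.4 (0.2/0.25 = 0.8, halved for two levels), correlation 0.5, 9 sessions, alpha 0.025, power 0.95. Section 10.4.2 gives the alpha as two-tailed.

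The repeated-measures ANOVA test of a two-level between factor has noncentrality

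λ = f² · N · m / (1 + (m − 1)ρ), on 1 and N − 2 degrees of freedom.

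- N = 56, m = 9: λ = 0.16 × 56 × 9 / (1 + 8 × 0.5) = 80.64 / 5 = 16.13. Power is 0.9535.
- N = 55: λ = 79.2 / 5 = 15.84. Power is 0.9498, just short of 0.95.

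This reproduces the stated 56 exactly, as one fixed-sample test that spends the whole 0.025 once. The same formula gives 48 at alpha 0.05 and 63 at alpha 0.0125. The 56 therefore includes no sequential adjustment.

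**Step 2. Overall error if 0.025 is used at both planned looks**

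Assumptions: 60 is the last analysis, either look can declare success, and information is proportional to subjects. The two test statistics then have correlation √(30/60) = 0.707 under the null. The two-sided critical value at 0.025 is z = 2.241.

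Overall error = 1 − P(|Z₁| < 2.241 and |Z₂| < 2.241) = 0.0428.

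| Meaning of 0.025 | Intended overall level | Overall error, looks at 30 and 60 |
|---|---|---|
| Overall level, applied at each look | 2.5% | 4.3%, about 1.7 times the intended level |
| Equal split of 0.05 over two looks | 5% | 4.3%, controlled |

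The error is the same on both rows. Only the level it is judged against changes, and the plan does not state that level.

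**Step 3. What a boundary would look like and cost**

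For an overall two-sided 0.025 and an O'Brien-Fleming-type Lan-DeMets spending function applied per side, the two-sided alpha spent at information fraction t is 4[1 − Φ(2.498/√t)], where 2.498 is the normal quantile for 0.025/4 = 0.00625.

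- At t = 30/60 = 0.5: 4[1 − Φ(3.532)] = 0.00082, so z = 3.345 and p < 0.0008.
- At 60: z = 2.246, p < 0.0247. Together the two looks return an overall error of 0.0250.
- Power, for an effect with 95% power in a fixed design (drift 2.241 + 1.645 = 3.886): 94.97%.

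The first threshold is sensitive to the information fraction, running from 0.0004 at 0.45 to 0.0025 at 0.60. This matters because Section 10.3 limits the data set to subjects completing at least 80% of the protocol, while Section 10.4.2 includes dropouts, so the analysed number at each look is open.

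**The case against.** The strongest reply is that 0.025 is half of 0.05, that exactly two formal looks are planned, and that the plan therefore already carries an equal split. On that reading the overall error is 4.3%, under 5%, and nothing is inflated. This stands as a possible reading, and it means inflation cannot be asserted. It does not close the gap. No section links 0.025 to the looks, and Section 10.5 uses it as the single alpha of a fixed-sample calculation.

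A second reply is that no section says a result at 30 would stop the trial. That is true: the list in Section 5.5 is general and is not tied to that look. Equally, no section rules it out for the formal analyses, although the plan does so expressly for the cohort reviews.

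A reader might go further and infer that 56 and 60 contradict each other, or that an additional final analysis follows 60 and carries the error past 5% even under an equal split. The documents do not support either inference. The 56 is a minimum, and 60 satisfies it; 60 is also the first whole number of six-subject cohorts at or above 56. Section 10.6.3 is a general unblinding statement and does not establish a later analysis. The available text gives no final N above 60, and the schematic and some front matter, where a target might appear, are not in it. What remains is a wording query: the 60-subject analysis is called interim and should be labelled.

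**Conclusion.** The point holds as a missing specification with a calculable consequence. Two formal efficacy analyses are planned without a boundary, per-look level or decision rule, and the sample size makes no allowance for them. If 0.025 is the overall level and is applied at both looks, the two-sided error is 4.3% instead of 2.5%. If it is an unstated equal split of 0.05, the error is 4.3% and controlled, provided 60 is the last analysis. The error rate is uncontrolled on one reading, and proven inflation should not be inferred. The figures assume that either look can declare success and that information accrues in proportion to subjects. The matter should be settled before the 30-subject data are unblinded, because a rule chosen afterwards would not be credible.

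**What to change.** First, state the overall two-sided alpha for the primary endpoint. If it differs from 0.05, say in Section 10.4.1 that it is an exception to the general level. State in Section 10.4.7.2 that the 60-subject analysis is the final one, or name the final N if it is not.

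Then choose one of two rules and refer to it in Sections 5.5 and 10.4.9:

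1. **Spend alpha.** Use an O'Brien-Fleming-type Lan-DeMets boundary, computed at the actual information fraction at each look. With overall 0.025 and looks at 30 and 60, the thresholds are p < 0.0008 and then p < 0.0247. Power is 94.97% against 95% for a fixed design, a loss of 0.03 percentage points.
2. **No claim at 30.** State that the 30-subject look cannot support an efficacy claim or early stopping for efficacy, and keep the full alpha for the final analysis. This costs no power.

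Either option is a change of protocol and SAP wording only.
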